The latest ESC guidelines from 2013 recommend to consider targeting the LV lead to an area of late activation in the left ventricle (**IIb, level B**) (6). This is based on the TARGET study including 220 patients (7). In this study, the site of latest mechanical activation was identified by echocardiography. Both the primary endpoint (reduction in left ventricular end systolic volume (LVESV) after 6 months) and the secondary endpoint, clinical response rate, turned out in favour of LV lead positioning corresponding to the latest activation. However, it is a major limitation in the TARGET study that in 15% of the patients in the control group the LV lead was positioned in scar tissue and in 14% the LV lead was in an anterior, anteroseptal, or inferoseptal position. Such LV lead positions are associated with a poorer effect of CRT and a poorer patient outcome. Thus, the control group was not treated according to daily standard in Danish CRT-implanting centres. This may play a substantial role in explaining the study result.

Furthermore, it is recommended that the LV lead is not positioned apically as this is associated with a poorer outcome (**IIa, level B**) (6, 8, 9). The randomised STARTER study of 187 patients showed a lower incidence of the endpoint "*HF hospitalisation or death*" with placement of the LV lead in a position corresponding to the latest mechanical LV activation as guided by echocardiography (10). Also in this study the LV lead position in the control group was far from optimal, 33% were placed apically and 15% anterolaterally. Thus, suboptimal treatment of the control group may also have influenced these study results substantially.

In a double-blind, randomised trial conducted at Aarhus University Hospital we studied targeted positioning of the LV lead to the coronary sinus (CS) branch closest to the latest mechanically activated area of the left ventricle. (11). We included 182 patients with heart failure (HF) and LBBB. Responders were defined as patients reaching the composite endpoint: alive **and** no heart failure admissions **and** increase in either

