NYHA class (\geq class 1) or $\geq 10\%$ increase in 6MWT (6-minute walk test) after 6 months. We found a higher clinical response rate (74% vs 58%, $p=0.02$) in the intervention group, but no difference in HF hospitalisation or death, nor after 1.8 years. Measured by the change in LVEF and LV dimension the effect of CRT was marked (LVEF increase from 25% to 37% in mean), and equal in the two treatment arms. In our control group, the LV lead was positioned in the first priority CS branch in 65% of the patients versus 83% in the intervention group, and only 3% were positioned apically or in scar tissue. With a more optimally treated control group the effect of LV lead positioning guided by echocardiography seems less pronounced.

Several observational studies, including post-hoc analysis of data from the above mentioned trial, suggest that a very late local electrical activation coinciding with LV lead position is associated with a better clinical and echocardiographic outcome (12, 13) (Europace abstract 002132, 2016, appendix 1). In daily clinical practice in Denmark the LV lead is typically placed in a posterolateral position with a relatively late local electrical activation in LBBB. The LV lead is not positioned to pace in an apical or anterior site unless this is where the very late activation is found after abandoning other potential target branches (due to high pacing threshold, phrenic nerve pacing or unstable lead position). Based on the existing literature, some physicians already search for late activation when positioning the LV lead, even though this strategy has not been tested in a controlled design.

Detailed mapping for a late activation may give rise to extended operating times, increased risk of infection, use of more electrodes and more hardware, which increases the costs, and increases radiation exposure for patient and staff. Furthermore, one may have to accept a higher threshold in a very late activated area which will reduce battery longevity of the device. It has not been settled, whether targeting towards the latest activation that may in some patients be close to scar tissue can be pro-arrhythmic.

At present, it is completely unsettled whether targeted positioning of the LV lead to the latest electrically activated area of LV is superior to current standard CRT with the LV lead preferentially in a non-apical posterolateral position with regard to improving patient prognosis (death or hospitalisation for heart failure).

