- Participation in another clinical trial of experimental treatment (does not include studies e.g. randomising patients to one of more stent types for PCI and following patients registry-based). Patients included in the national trial of hydralazine and metformin for heart failure may also be included
- Contraindication for establishing implantable device treatment
- Previously implanted CRT system
- Does not wish to participate

Endpoints:

Primary:

- Death or non-planned hospitalisation for heart failure
 - Death
 - Non-planned hospitalisation for heart failure (non-planned hospitalisation >24 hours due to heart failure requiring intensified heart failure therapy)

Secondary:

- Sudden death
- Cardiac death
- Clinical response defined as "*increase in NYHA class (≥ 1 class from baseline) or improved walking distance by 6MWT ($\geq 10\%$ from baseline)*" after 6 and 24 months
- 6MWT, changes from baseline to follow-up after 6 and 24 months
- NYHA class, changes from baseline to follow-up after 6, and 24 months
- Quality of Life (QoL) and patient reported outcomes (PROs), changes from baseline to follow-up after 6, 12, 24 and 48 months
- Echocardiographic endpoints (re-modelling of LV: LVESV, LVEDV, LVEF). See supplementary protocol on imaging
- ICD therapy (time to first and number of appropriate and inappropriate ICD therapy, respectively, in addition as ATP and shock therapy, respectively)
- Time to first episode of VT/VF
- Persistent atrial fibrillation
- Recently diagnosed atrial fibrillation (>30 seconds recorded by the implanted device)
- Procedure time at implantation, fluoroscopy time and dose
- Number of LV leads used at implantation
- Device-related complications (periprocedural: lead re-operation, pneumothorax, hemothorax, pericardial bleeding/tamponade and later (30 days post implantation): LV lead re-operation, device replacement due to battery depletion, and infection requiring extraction)
- Battery longevity (measured by ¹number of device replacements during the study period due to battery depletion and ² device battery longevity + estimated remaining device battery longevity as reported by the device at last study follow-up)

Study design:

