Post implantation, prior to discharge, and in the set device mode (DDD or VVI) ECG-12 with CRT, ECG-12 with pure RV pacing, and ECG-12 with pure LV pacing are recorded. At each follow-up ECG-12 is recorded when the patient arrives, with the existing device settings. The interval from RV pacing to activating the LV lead is measured at each follow-up visit. ECG's are recorded and stored digitally.

At each visit, the patient's current medication is recorded.

Patient-reported outcomes (PRO's):

At baseline and again after 6, 12, 24 and 48 months the following questionnaires will be used:

Kansas City Cardiomyopathy Questionnaire (KCCQ-12), 12 items

Patient Health Questionnaire (PHQ-9), 9 items

Generalized Anxiety Disorder (GAD-7), 7 items

At baseline in addition:

Expectations towards ICD therapy (EXPECT-ICD), 10 items

Brief Illness Perception Questionnaire (BIPQ), 9 items

Resulting in 47 items at baseline and 28 items after 6, 12, 24 and 48 months.

Details regarding PRO's shown in the PRO-appendix.

All patients are followed until the last included patient has been followed for at least 2 years.

If, at 3 months after implantation, there is no clinical response (defined as "*no improvement in NYHA class and <10% improvement of the 6MWT walking distance*") AV and VV optimisation guided by echocardiography is done in both groups. A separate protocol will be prepared for this optimisation.

In patients, who develop or have persistent atrial fibrillation, where sinus rhythm is not immediately obtained by medication and/or by DC cardioversion, there is a risk of a large frequency of intrinsic conducted ventricular activations without effective CRT. If effective CRT drops to <95% the patients are offered ablation of the AV node (His-ablation) or pulmonary vein isolation at the follow-up physician's discretion for the purpose of re-establishing effective CRT close to 100% of the time. If patients develop frequent ventricular extrasystoles that compromise effective CRT (to <95%), ablation for ventricular extrasystoles or medical antiarrhythmic treatment is offered at the follow-up physician's discretion. Atrial fibrillation and ventricular extrasystoles are handled equally in the two treatment arms.

Sample size:

Power calculation:

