Based on previous studies as well as data from the CRT population at Aarhus University Hospital, Skejby (n=1600) it is assumed that 35% of the population will reach the primary endpoint "death or non-planned hospitalisation for heart failure" within a period of 4 years. Based also on the above mentioned randomised controlled trial of 182 patients and up to 3 years of follow-up, and on the result of the DANISH study, this seems realistic (15). Half of these endpoints are expected to be deaths and the other half of non-planned hospitalisation for heart failure. To show a relative reduction of 25% in the incidence of this endpoint (to an absolute 26%) with $\alpha=0.05$ and $1-\beta=0.80$, n=432 patients must be included in each group. Given these

assumptions, 264 primary endpoints will occur during the study period. Assuming that no more than 10% of the patients withdraw during the study period, it will be sufficient to **include n=500 patients in each group**. Thus, a total of n=1000 patients need to be included in the study. The study is not designed to detect a significant reduction in mortality.

If, alternatively, one wanted to show a 20% reduction (from 35% to 28%), 719 patients should be included in each group (453 primary endpoints), 1500 patients in total. If one wanted to show a 30% reduction (from 35% to 24.5%) 315 patients should be included in each group, 700 in total.

Data analysis:

The primary analysis is carried out as an intention-to-treat analysis (patients randomised to the intervention group are compared with patients randomised to the control group without regard for their actual treatment). The primary data analysis will present time to the primary endpoint in Kaplan-Meier curves for each treatment group and if relevant stratification variable. Hazard ratio for reaching the primary endpoint in the intervention group relative to the control group is calculated by use of Cox regression model. Supplementary, restricted mean survival time is calculated.

Besides a non-adjusted analysis, also an analysis adjusted for age, gender, QRS morphology (LBBB/non-LBBB/RV paced), QRS width (≥ 150 ms / < 150 ms), NYHA class (II/III or outpatient IV), underlying disease (IHD/non-IHD determined heart failure), as well as including centre is done.

Subgroup analyses of the primary endpoint are planned for patients

- with different gender
- with higher and lower age (around the median)

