- with QLV (time from QRS start to local LV activation where the LV lead is positioned) above/below the median value, respectively
- in NYHA class II and III/outpatient IV, respectively, at baseline
- with baseline LVEF above/below the median value, respectively
- with ischaemic and non-ischaemic background for heart failure, respectively
- with LBBB and non-LBBB, respectively
- with upgrade from RV pacing to CRT and primary implantation of CRT, respectively
- with the RV lead in a septal and non-septal position, respectively (RV lead position determined by flash CT after implantation)

- with the RV lead in an apical and non-apical position, respectively (RV lead position determined by flash CT after implantation)
- with and without echocardiography detected dyssynchrony, respectively (radial time-to-peak, cross-correlation and pattern-analysis) of LV
- scar tissue/perfusion evaluation by CT scan. Total percentage of scar tissue (higher/lower than median) as well as impact of scar tissue localisation with regard to the site of LV lead position (LV lead close to scar (in or in neighbour-segment in a 17-segment model of LV) or remote to scar.

Analysis for statistical interaction is done with respect to the subgroup-analysis above and presented graphically in a Forest plot.

Secondary endpoints are compared in a similar way using Cox regression or multipel linear or logistical regression analysis. In datasets with repeated measures, ANOVA is used. Whether data are normally distributed or not and whether single or repeated data determinations exist are taken into consideration. If relevant, competing risk is adjusted for in the analyses.

A p-value <0.05 is considered significant in two-sided test.

Adjudication of endpoints:

Monthly during the study/follow-up, the study secretariat will verify vital status for all included patients through the Civil Registration System (CPR). In case of death, the centre following the patient will gather information on the death from the patient's GP and from other hospitals/departments, if relevant. This information will be forwarded to the study secretariat coordinating the adjudication of endpoints. A copy of the death certificate is obtained, unless the cause of death is known (e.g. during hospital admission).

The endpoint committee consists of the members of the steering committee.

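### Clinical response is worded so that a worsening NYHA class counts as response, and the plan does not say how patients who die before the 6- or 24-month visit are classified

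*Combined protocol and SAP*

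**What the plan says.** In the Combined protocol and SAP, the Secondary list under Endpoints defines clinical response at 6 and 24 months as "increase in NYHA class (≥ 1 class from baseline) or improved walking distance by 6MWT", with a 10% threshold for the walking test. No condition on survival or heart-failure admission is attached.

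Three other places bear on it:

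- **Follow-up**, paragraph on patients without response at 3 months: absence of clinical response is "no improvement in NYHA class and <10% improvement of the 6MWT walking distance".
- **Background**, on the group's previous trial ("We included 182 patients with heart failure (HF) and LBBB"): "Responders were defined as patients reaching the composite endpoint: alive", together with "no heart failure admissions" and a functional criterion at 6 months. That functional criterion also speaks of an increase in NYHA class. The result was: "We found a higher clinical response rate (74% vs 58%, $p=0.02$) in the intervention group".
- **Data analysis**: "The primary analysis is carried out as an intention-to-treat analysis". For the rest, "Secondary endpoints are compared in a similar way using Cox regression or multipel linear or logistical regression analysis", with competing risk to be handled where relevant and no endpoint named.

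The substantial amendments listed in the separate amendment document do not change this definition.

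**The concern.** There are two separate defects.

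The first is direction. The trial enrols NYHA II, III and outpatient IV and excludes class I, so a rise of one class is a deterioration. This is the governing definition of a binary endpoint, and analysis code written to it would label some worsened patients as responders and some improved patients as non-responders.

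The second is a missing rule. A patient who dies before the visit has neither component. Nothing says whether that patient is a non-responder, missing or excluded. Ordinary logistic regression software would drop the record. If the trial hypothesis is right, the number dropped would differ by arm, and the comparison would no longer be between the groups as randomised. If the choice is left until results are known, it becomes a post-hoc choice.

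**Working it through.** **Direction.** The endpoint as written can be set beside the 3-month rule for four patterns of change from baseline:

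| NYHA change | 6MWT gain | Endpoint as written | Direction of the 3-month rule |
|---|---|---|---|
| III to II | under 10% | non-response | response |
| II to III | under 10% | response | non-response |
| none | under 10% | non-response | non-response |
| any | 10% or more | response | response |

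The two definitions disagree exactly where the NYHA class changes and the walking gain is under 10%. The documents give no distribution of NYHA change, so the number misclassified cannot be stated.

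**Deaths: inputs.** The plan attaches no figure to this endpoint, so the rates come from the Sample size section: 35% control events at 4 years, a 25% relative reduction, half of the events being deaths, and 500 patients per arm. That section reproduces. For 35% versus 26%, two-sided alpha 0.05 and power 0.80, the two-proportion formula gives 410 per group, or 432 with continuity correction (stated: 432). Expected events are 432 × (0.35 + 0.26) = 263.5 (stated: 264).

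**Deaths: calculation.** Two assumptions are added: a constant hazard, and the same half share of deaths in both arms. The 4-year intervention rate is 0.35 × 0.75 = 26.25%. Cumulative events at month m are 1 − (1 − p)^(m/48), and first-event deaths are half of that.

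| | Control | Intervention |
|---|---|---|
| Any primary event, 6 months | 1 − 0.65^(1/8) = 5.2% | 1 − 0.7375^(1/8) = 3.7% |
| Death as first event, 6 months | 2.6% (13 of 500) | 1.9% (9 of 500) |
| Any primary event, 24 months | 1 − 0.65^(1/2) = 19.4% | 1 − 0.7375^(1/2) = 14.1% |
| Death as first event, 24 months | 9.7% (48 of 500) | 7.1% (35 of 500) |

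Applying the formula to control deaths alone (17.5% at 4 years) gives 1 − 0.825^(1/2) = 9.2% at 24 months and 2.4% at 6 months. Hence about 9-10% at 24 months. Deaths that follow a heart-failure admission are not counted as first events, so total deaths could be higher.

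**Effect on the comparison.** Suppose the response rate r among survivors is equal in both arms, with r assumed between 58% and 74% (the two rates of the previous trial). A survivors-only comparison then shows a difference of 0. Counting death as non-response shows r × (control deaths − intervention deaths):

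- 24 months: 0.58 × 0.0263 = 1.5 points to 0.74 × 0.0263 = 1.9 points.
- 6 months: 0.58 × 0.0075 = 0.4 points to 0.74 × 0.0075 = 0.6 points.

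If heart-failure admission is also counted as non-response, and the same r applies to event-free patients, the shift is r × 0.0526 = 3.0 to 3.9 points at 24 months and r × 0.0151 = 0.9 to 1.1 points at 6 months.

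All these shifts depend on the mortality effect. If the benefit fell wholly on admissions, deaths would be about equal and the shift from counting deaths would be about nil.

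**The case against.** The strongest reply is that the NYHA wording is a slip whose intent is plain. The 3-month rule shows that improvement is meant, and the Background describes the previous trial's responders with the same word while reporting a favourable result. NYHA change and 6MWT change are also separate secondary endpoints, so the true direction would be visible. All of this stands as evidence of intent, and it makes the correction easy. It does not make the written definition right. It also rules out reading the NYHA direction as a departure from the previous trial.

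On deaths, a reader might infer that the plan compares survivors only. The documents do not say so. They are silent, and dropping out is the likely default. Secondary endpoints are to be compared in a way similar to the intention-to-treat primary analysis, but intention to treat does not by itself assign a response status to a patient who has died.

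A reader might also infer that everyone with a primary event, about 14% to 19% by 24 months, is lost. That does not follow: admitted patients who are alive can still be assessed and stay in the comparison.

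Finally, leaving heart-failure admission out of the definition is defensible. Death and heart-failure hospitalisation already form the primary endpoint, and a composite that repeats both would partly re-test it. The plan nowhere commits this endpoint to reproducing the earlier 74% versus 58%, which came from LBBB patients with mechanical targeting. This part of the reply stands in full.

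**Conclusion.** The NYHA component is wrong as written and conflicts with the Follow-up section. It needs correcting even though the intent is clear. It would be too strong to call the whole endpoint inverted, because the walking-test component is correct and settles the classification of anyone who gains 10% or more.

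The handling of death is unspecified, although the previous trial specified it. The consequence is modest at 24 months and small at 6 months. The sizes rest on the plan's planning rates, a constant hazard, an equal share of deaths in both arms and equal symptom response among survivors. None of these is a finding about the trial's data. This is one secondary endpoint, and the primary analysis and sample size are untouched.

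**What to change.** 1. Reword the endpoint as an improvement (decrease) of at least one NYHA class, or a gain of at least 10% in 6MWT distance, from baseline.
2. State that all randomised patients are analysed and that death before the 6- or 24-month visit counts as non-response. Say separately how living patients without an assessment are handled.
3. Show the functional result among survivors as a supplementary table.
4. Optionally, give the previous trial's composite, which also requires no heart-failure admission, as a sensitivity analysis. It need not replace the endpoint.

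No new data are needed. NYHA class and 6MWT are scheduled at both visits, vital status is checked monthly and admissions are adjudicated. The cost is a few lines of text and a slightly lower response rate in both arms. The amendment document extends the study period through 31-12-2026 and is itself dated May 2026, so the change should be recorded as a dated clarification before any unblinded analysis.

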A standard implantation of a CRT system is associated with a non-negligible risk of complications (16). It is unknown, whether this risk will be higher in the intervention group, where mapping of the activation in CS is done. This mapping is expected to prolong the implantation procedure, and it is uncertain, whether the more extensive handling of guiding sheaths, guide wires and leads will increase the complication risk with respect to CS dissections/perforations, bleedings or infections. In a pilot study at Aarhus University Hospital, we recorded no more complications at procedures including mapping of activation in the CS branches. In the present planned study, all implantation related complications are recorded in both treatment groups. Only patients with indication for CRT according to the current guidelines are offered participation in the study. Based on the existing literature, it is expected that the intervention including positioning of the LV lead after mapping of the CS branches will potentially increase the percentage of patients that benefit from CRT and improve the prognosis in the patient cohort treated with CRT. A positive

study result confirming the study hypothesis will lead to a changed implantation strategy in patients with indication for CRT, nationally and internationally.

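### The device-complication endpoint does not match the harms the protocol names as possible results of coronary sinus mapping

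*Combined protocol and SAP*

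**What the plan says.** In the combined protocol and SAP, the secondary endpoints define device-related complications by two sub-lists, an early (periprocedural) one and a later one. Together they run: "lead re-operation, pneumothorax, hemothorax, pericardial bleeding/tamponade and later (30 days post implantation): LV lead re-operation, device replacement due to battery depletion, and infection". The infection item is limited to infection that requires extraction. Nothing in the wording marks either list as illustrative, so both read as closed. Battery-depletion replacement appears again in the next endpoint, battery longevity.

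The section on ethical considerations says of procedural risk: "It is unknown, whether this risk will be higher in the intervention group, where mapping of the activation in CS is done". It calls it uncertain whether the extra handling of sheaths, wires and leads "will increase the complication risk with respect to CS dissections/perforations, bleedings or infections". It reports from a pilot study that "we recorded no more complications at procedures including mapping of activation in the CS branches", without numbers, and states that "all implantation related complications are recorded in both treatment groups". The Background says: "Detailed mapping for a late activation may give rise to extended operating times, increased risk of infection".

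The Data analysis section gives a general rule for secondary endpoints (Cox, linear or logistic regression, two-sided 0.05) and nothing specific to complications. Blinded adjudication is described for the primary endpoint and for cause of death. The list of amendments records no change to this endpoint.

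**The concern.** The procedures differ in one step: the CS branches are mapped in the intervention arm and not in the control arm. A harm caused by that step should show in the complication endpoint. If the endpoint omits the events that the step is thought capable of causing, the trial could report similar complication rates while those events differ.

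Events that are recorded but assigned to no endpoint have no fixed definition and no planned comparison. Which of them to report, and how, would then be decided later, possibly with results known. A fixed definition matters more here because the implanting physician knows the arm and no blinded adjudication of complications is described.

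**Working it through.** **Step 1. Named harms against the endpoint.** The harms come from Background and Ethical considerations, the components from Endpoints, Secondary.

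| Harm named as possible | Counted in the endpoint? |
|---|---|
| CS dissection | Only if pericardial bleeding/tamponade, hemothorax or lead re-operation follows |
| CS perforation | Same condition |
| Bleeding | Pericardial and pleural bleeding yes; other bleeding (for example at the pocket) no |
| Infection | Only in the later list, and only if it requires extraction |

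**Step 2. The time windows.**

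- *After day 30.* This is the more natural reading, given the word later and the battery-depletion item. Infection in the first 30 days is then in no list as infection. This holds even if the periprocedural period is taken to run to day 30, because the early list has no infection item.
- *Within 30 days.* Early infection requiring extraction counts, but infection after day 30 does not, and the battery-depletion item makes little sense.
- *Either reading.* Infection treated without extraction is never counted.

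**Step 3. What can be calculated.** The documents give no rate, power or sample size for complications, so there is no plan figure to reproduce for this endpoint. The planned size is 500 per group. (The efficacy calculation behind it does reproduce: 35% vs 26%, two-sided 0.05, power 0.80, with continuity correction, gives 432 per group. It has no bearing here.)

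The figures below use **assumed** rates and only show the range. With n = 500 per arm and p̄ the mean of the two rates:

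power = Φ{ (|p1 − p2| − 1.96·SE0) / SE1 }, where SE0 = √[2p̄(1 − p̄)/n] and SE1 = √[(p1(1 − p1) + p2(1 − p2))/n].

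Example, 2% vs 5% (500 × 0.02 = 10 events against 500 × 0.05 = 25): p̄ = 0.035, SE0 = √(2 × 0.035 × 0.965/500) = 0.0116, SE1 = √[(0.0196 + 0.0475)/500] = 0.0116, and (0.03 − 1.96 × 0.0116)/0.0116 ≈ 0.62, so power is about 0.73.

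| Assumed rates of the omitted events | Power, compared on their own |
|---|---|
| 1% vs 2% | 0.255 |
| 1% vs 3% | 0.618 |
| 2% vs 4% | 0.458 |
| 2% vs 5% | 0.733 |

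Left out of the endpoint, such an excess gives an expected difference of zero in it.

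Pooled into one composite whose other items occur equally in both arms:

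| Rate of other items | Added 1% vs 3% | Added 2% vs 5% |
|---|---|---|
| 3% | 0.305 | 0.486 |
| 5% | 0.235 | 0.398 |
| 8% | 0.182 | 0.318 |

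For extraction-requiring infection at an assumed 1% vs 2%, losing 25%, 50% or 75% of cases in both arms to the uncounted period lowers power from 0.255 to 0.202, 0.148 or 0.095. The normal approximation is rough at such counts.

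**The case against.** Five points can be made for the plan.

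1. *Other endpoints bear on safety.* A reader might infer that this is the trial's only safety comparison. It is not. Sudden and cardiac death, VT/VF, ICD therapy, procedure and fluoroscopy time, number of LV leads and battery longevity are also secondary endpoints, and death is part of the primary. This stands. But none of these counts a dissection, a pocket bleed or an infection, and this is the only complication endpoint.

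2. *Some of the harm is captured, and the risk is uncertain.* A reader might infer that bleeding is left out altogether, or that the trial misses the main risk of mapping. Pericardial bleeding and hemothorax are listed, the protocol calls the added risk uncertain, the pilot saw no excess, and no document ranks the risks. What remains is dissection or perforation without the listed consequences, other bleeding, and part of infection.

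3. *The 30-day gap is one reading.* A reader might infer that an extraction for infection on day 15 is lost. That is not established. The early list does not restrict lead re-operation by cause, so such an extraction might count there. It would still not be counted as infection.

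4. *The data are collected and a Safety Committee exists.* A reader might infer a failure of data collection. The protocol says all implantation-related complications are recorded in both arms. The gap lies in the endpoint definition: nothing supplied gives the omitted events a planned comparison. The case record form was not available.

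5. *It is late to change an endpoint.* The amendments run the study through 31-12-2026, and Follow-up requires at least 2 years for the last patient. That puts the last inclusion at about the end of 2024, while the amendments document is dated 2026. Events around implantation should therefore already have occurred. This stands and shapes the fix, as does the power lost by pooling.

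**Conclusion.** The concern holds as a mismatch of definition. The protocol poses a safety question about CS dissection or perforation, bleeding and infection, and its only complication endpoint answers that question in part. An excess confined to the omitted events would leave the endpoint unchanged in expectation.

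The size in this trial is unknown. The assumed rates above show only that a separate comparison could have anything from low to moderate power (about 0.25 to 0.73). The conclusion rests on two assumptions: that the two lists are closed, as they read, and that no document outside those supplied adds the missing events. It does not depend on which meaning of the 30-day label was intended, since each leaves part of infection uncounted.

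**What to change.** - From the complications the protocol says are recorded in both arms, add CS dissection/perforation, other recorded bleeding, and infection at any time from implantation. Report each as its own component, with a between-arm comparison by component. Do not rely on a single pooled composite.
- Define the two windows as contiguous: day 0-30 and after day 30.
- Report battery-depletion replacement once, under battery longevity.
- Keep the existing list as a reported analysis. If the change is made after the events have occurred, label the added components as supplementary. Fix the definitions before the results are examined by arm.

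The cost is wording and extra tables. The overall complication rate will be higher in both arms, and rare components will have low power, so estimates with confidence intervals will say more than tests. Infections treated without extraction can be included only as far as they were recorded; a commitment to record implantation-related complications does not guarantee that late ones were.
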